### **11.4. Concomitant Medications and Procedures**

The start and stop dates, dose, unit, frequency, route of administration, and indication for all prior and concomitant medications, nondrug therapies (eg, blood transfusions, oxygen supplementation, physical therapy, etc) and other procedures will be recorded in the eCRF.

## **11.5. Safety Laboratory Tests**

Results of CMP and CBC with differential, collected for clinical purposes, will be abstracted from the medical record. If such results are not available, blood samples for research purposes will be collected only as part of a clinically necessary venipuncture. Clinical sample analysis for CMP and CBC with differential studies will be performed at the institution's local laboratory.

Investigators must review and sign laboratory reports and document the clinical significance of any laboratory abnormalities. New, clinically significant laboratory abnormalities or clinically significant changes in laboratory values will be reported as AEs.

## **11.6. Immunological Assays and Archival Samples**

Panel reactive antibodies (PRA), anti-BSA antibody and archival samples will be obtained prior to StrataGraft application from all enrolled subjects. Samples for the assessment of PRA and anti-BSA antibodies will also be obtained between Week 7 and Month 6 for all treated subjects.

Specific instructions for collection, processing, storage, and shipment of these samples will be provided in the Laboratory Manual.

## **11.7. Pain Assessment**

The EVENDOL pain assessment scale, a tool validated in preverbal children, will be used to assess pain in enrolled subjects up to 5 years of age (inclusive). The EVENDOL scale is designed such that it can be completed by an observer (eg, parent) based upon outward behavioral manifestations such as crying, facial expressions, movements and posturing as well as environmental interactions ([Fournier-Charrière, 2012](#)).

The FPRS (FACES pain rating scale), a well-documented and validated tool, will be used to assess pain in enrolled subjects older than 5 years of age. The FPRS is demonstrated to effectively evaluate pain using a Likert-like scale of facial expressions, which are converted into numeric values to obtain a quantitative assessment of pain ([Wong, 1998](#)).

Details regarding administration of the pain assessment tools are provided in the Manual of Procedures.

## **11.8. Assessment of the Need for Continued Hospitalization**

At each study visit subsequent to Day 1 but prior to hospital discharge, an assessment of the need for continued hospitalization will be completed. Investigators will be asked to identify the reason(s) for continued hospitalization including: pain management, fluid or nutritional status, infection risk, ongoing infection, inability to perform activities of daily living, insufficient social support, or other issues.

## 11.9. Adverse Events and Serious Adverse Events

### 11.9.1. Definitions

#### 11.9.1.1. Adverse Event (AE)

An AE is any untoward or undesirable medical occurrence in a subject who is administered a study treatment, which does not necessarily have to have a causal relationship with this treatment. An AE can therefore be any unfavorable and unintended sign (including an abnormal laboratory finding), symptom, or disease (new or exacerbated) temporally associated with the use of study treatment.

Examples of AEs include but are not limited to:

- Any abnormal laboratory test results (hematology, clinical chemistry, or urinalysis) or other safety assessments (eg, ECG, radiological scans, vital signs measurements), including those that worsen from baseline, considered clinically significant in the medical and scientific judgment of the investigator (ie, not related to progression of underlying disease).
- Exacerbation of a chronic or intermittent pre-existing condition including either an increase in frequency and/or intensity of the condition.
- New conditions detected or diagnosed after study treatment administration even though it may have been present before the start of the study.
- Signs, symptoms, or the clinical sequelae of a suspected drug-drug interaction.
- Signs, symptoms, or the clinical sequelae of a suspected overdose of either study treatment or a concomitant medication. Overdose per se will not be reported as an AE/SAE unless it is an intentional overdose taken with possible suicidal/self-harming intent. Such overdoses should be reported regardless of sequelae.
- “Lack of efficacy” or “failure of expected pharmacological action” per se will not be reported as an AE or SAE. Such instances will be captured in the efficacy assessments. However, the signs, symptoms, and/or clinical sequelae resulting from lack of efficacy will be reported as AE or SAE if they fulfill the definition of an AE or SAE.

Events that do **not** meet the definition of an adverse events include:

- Any clinically significant abnormal laboratory findings or other abnormal safety assessments which are associated with the underlying disease, unless judged by the investigator to be more severe than expected for the participant’s condition.
- The disease/disorder being studied or expected progression, signs, or symptoms of the disease/disorder being studied, unless more severe than expected for the participant’s condition.
- Medical or surgical procedure (eg, endoscopy, appendectomy): the condition that leads to the procedure is the AE.

- Situations in which an untoward medical occurrence did not occur (social and/or convenience admission to a hospital).
- Anticipated day-to-day fluctuations of pre-existing disease(s) or condition(s) present or detected at the start of the study that do not worsen.
- Failure to achieve complete wound closure by Week 12.

#### **11.9.1.2. Unexpected Adverse Event**

An unexpected AE is an AE which exhibits a different nature or severity than those identified in the Investigator's Brochure or has not previously been noted in relationship to StrataGraft.

#### **11.9.1.3. Treatment Emergent Adverse Events**

Treatment-emergent AEs are defined as those that are not present at start of study treatment or that represent the exacerbation of a pre-existing condition during the treatment-emergent period. The treatment-emergent period is defined as the time from the application of StrataGraft to the end of the study.

#### **11.9.1.4. Serious Adverse Event (SAE)**

An SAE is defined as any untoward medical occurrence that results in any of the following outcomes:

##### **Death**

Death is an outcome of an event. The cause of death should be recorded and reported on the SAE Form. All causes of death must be reported as SAEs. The investigator should make every effort to obtain and send death certificates and autopsy reports to the Sponsor or designee, or state not available. See Section 4.4 for xenotransplantation considerations.

##### **Life-threatening**

An adverse event or suspected adverse reaction is considered "life-threatening if, in the view of either the investigator or Sponsor, its occurrence places the subject at immediate risk of death. It does not include an AE or suspected adverse reaction that, had it occurred in a more severe form, might have caused death. For example, hepatitis that resolved without evidence of hepatic failure would not be considered life-threatening, even though hepatitis of a more severe nature can be fatal. Similarly, an allergic reaction resulting in angioedema of the face would not be life-threatening, even though angioedema of the larynx, allergic bronchospasm, or anaphylaxis can be fatal.

##### **Inpatient hospitalization or prolongation of existing hospitalization**

Hospitalization is defined as an admission to a hospital. The following situations should not be reported as SAEs:

- A hospitalization or prolongation of hospitalization is needed for a procedure required by the protocol.

- A hospitalization or prolongation of hospitalization is part of a routine procedure followed by the center (eg, stent removal after surgery). This should be recorded in the study file.
- A hospitalization for a pre-existing condition that has not worsened.

### **Persistent or significant incapacity**

The term disability means a substantial disruption of a person's ability to conduct normal life functions.

This definition is not intended to include experiences of relatively minor medical significance such as uncomplicated headache, nausea, vomiting, diarrhea, influenza, and accidental trauma (eg, sprained ankle) which may interfere with or prevent everyday life functions but do not constitute a substantial disruption.

### **Congenital anomaly or birth defect**

After enrollment and follow up in this study, any pregnancy reported to occur will be followed to conclusion and all live-born children will be followed for 28 days following birth. Any congenital anomaly or birth defect will be reported.

### **Important Medical Events**

Important medical events that may not result in death, be life-threatening, or require hospitalization may be considered serious when, based upon appropriate medical judgment, may jeopardize the subject or the subject may require medical or surgical intervention to prevent one of the outcomes listed above. Examples of such medical events include allergic bronchospasm requiring intensive treatment in an emergency department or at home, blood dyscrasias or convulsions that do not result in inpatient hospitalization, or the development of drug dependency or drug abuse.

### **Anticipated Adverse Events**

Adverse events (serious or nonserious) that commonly occur in the study population or background regimen will be considered anticipated events. Such events include known consequences of the condition under investigation (eg, symptoms, disease progression) and other events that may be common in this study population. A list of anticipated events for this study population is provided in the Investigators Brochure. Anticipated events are to be recorded in the eCRF and reported as SAEs when serious. These SAEs will not be expedited to health authorities, but rather, included in aggregate safety reports.

#### **11.9.1.5. Adverse Event of Special Interest**

An adverse event of special interest (serious or nonserious) is one of scientific and medical concern specific to the sponsor's product or program, for which ongoing monitoring and rapid communication by the investigator to the sponsor can be appropriate. AESI will be reported using the SAE/AESI Report Form and observe the same reporting timeline ([Table 6](#)). For this study, Adverse Events of Special Interest (AESI) include:

- Signs/symptoms of endotoxin reaction (ie., combination of hypo/hyperpyrexia, hypo/hypertension, tachycardia, tachypnea, and change in mental status) within 24 hours after StrataGraft application
- Unexpected or unusual infections
- Dermatological malignancy

If any of the above occurs, the event will be reported within 24 hours of first knowledge of the event and follow-up reports provided as changes in the event occur. Photographs will be taken of the affected wound(s) to document the AESI.

#### **11.9.2. Adverse Event Medical Management Plan**

In the event of an AE, the investigator will use accepted standard of care (medication or surgery) as needed. A tiered approach will be used for the medical management of complications specific to the study burn sites, as described below:

- Initial management of local infection or immune reactions with topical antimicrobials or anti-inflammatory agents, respectively.
- Systemic antibiotics or anti-inflammatory medications administered for infections or immunological responses that fail to respond to topical therapy.
- For complications that do not respond to topical or systemic therapy, the treated wound may be excised and the complication managed with topical or systemic therapy, as necessary.
- Based on clinical judgment, autograft may be applied to the resulting wound bed to expedite wound closure.

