**Figure 1: Number and Etiology of Burns by Age**

Source: Figure 11, [National Burn Repository, 2019](#).

Although wound healing and wound management do not differ between adults and children, there are differences between children and adults that may significantly affect how pediatric burn patients are managed. Young children have nearly 3 times the surface area to body mass ratio of adults, so they experience greater evaporative water losses and, hence, require greater fluid replacement. This difference in the surface area to body mass ratio also predisposes the child to hypothermia and increases their thermogenic metabolic demand. Finally, because of disproportionately thin skin in children, a burn that may initially appear to be partial thickness may instead declare itself to be full thickness within a day or 2 of injury, making burn depth assessment difficult.

After stabilization of the critical care issues in the burn-injured child, attention is directed toward burn wound management. The ultimate aim of wound management in burns is to prevent wound infection and facilitate closure of the wounds, either spontaneously or by autologous skin grafts. Key elements of burn wound management include cleansing, debridement or surgical excision, topical antimicrobial agents, and dressings.

Regardless of the age of the patient, evidence suggests that early excision of burn eschar is effective in decreasing morbidity, improving the mortality rate, and reducing length of stay (Pietsch, 1985; Muller, 1994; Herndon, 1989), as well as hospital costs (Munster, 1994). Deep partial thickness (DPT) burns that are expected to take longer than 3 weeks to heal and full-thickness burns (with the exception of very small injuries) should be grafted, as this reduces hypertrophic scarring and results in better cosmesis (Heimbach, 1987; Chipp, 2017).

Excised areas are usually closed with autograft or with allograft, xenograft, or other skin substitute until autograft is available or the wound spontaneously closes. Availability of autologous donor tissue, however, is limited by the extent of the burn injury. In larger injuries, donor sites are often harvested repeatedly, increasing the likelihood of scarring at those sites. Further, the simple harvest of a donor site incurs acute pain as well as the potential for infection and scarring. As such, methods to reduce the amount of donor tissue needed to achieve wound closure are always sought.

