#### 5.1.2. Primary Efficacy Endpoint

Percentage of subjects achieving confirmed complete closure of StrataGraft treatment sites on or before Week 12 without autograft placement. Confirmed complete wound closure is defined as complete skin re-epithelialization confirmed at 2 consecutive visits at least 2 weeks apart but no later than Week 20.

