### **8.2.2. Prohibited Therapies**

Starting with Screening, the following treatments are not permitted:

- Application of any silver- or sulfa-containing topical agents (including mafenide acetate) or dressings to the StrataGraft treatment site through confirmed complete wound closure.
- Use of chlorhexidine- or iodine-based skin cleansers until confirmed, complete wound closure. Such cleansers may be used for wound preparation prior to StrataGraft application and must be thoroughly rinsed off prior to placement.
- Use of any investigational drug, device, or procedure administered as part of a research study.
- Use of laser therapy to scars located on the StrataGraft treatment site through completion of the Month 12 visit.

If any prohibited therapy is administered during the study, all pertinent information will be recorded. The designated study medical monitor must be informed immediately upon discovery of such use.

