To evaluate whether StrataGraft treatment eliminates or reduces the need for autografting and promotes wound closure in a pediatric population with thermal burns that contain intact dermal elements and for which autografting is clinically indicated.	All enrolled subjects who received StrataGraft	$H_0$ : The response rate of primary endpoint is less than or equal to the 50% $H_1$ : The response rate of the primary endpoint is greater than the 50%  Positive study criteria: The lower bound of primary endpoint 95% CI derived from the normal approximation to the binomial $> 50\%$ .	Percentage of subjects achieving confirmed complete closure of all StrataGraft treatment sites on or before Week 12 without autograft placement. Confirmed complete wound closure is defined as 100% re-epithelialization confirmed at 2 visits at least 2 weeks apart but before Week 20.	Early discontinuation due to: 
 
• Withdrawal of informed consent
 
• Lost to follow-up
 
• Adverse event
 
• Investigator decision
 
• Death
 
• Other
 
 Missing/incomplete data will be imputed as failure (ie, no confirmed complete wound closure).

CI = Confidence Interval; LB = Lower Bound

**Table 8: The Objective, Population, Hypotheses, Endpoints and Intercurrent Events and Data Handling for Ranked Secondary Efficacy Endpoints**

Objectives	Population	Hypotheses	Endpoints	Intercurrent events and data handling
To evaluate the mean averaged percent of wound area closure of StrataGraft treatment site without autograft placement at Week 12	All enrolled subjects who received StrataGraft	$H_{01}$ : Mean of averaged percent wound area closure of StrataGraft treatment site without autograft placement at Week 12 $\leq 50\%$ $H_{11}$ : Mean percent of wound area closure of StrataGraft treatment site without autograft placement at Week 12 $> 50\%$	Mean of averaged percent area of StrataGraft treatment site closed without autograft placement at Week 12	
Early discontinuation due to:
 
 
• Withdrawal of informed consent
 
• Lost to follow-up
 
• Adverse event
 
• Investigator decision
 
• Death
 
• Other
 
 
Missing/incomplete continuous variables will not be imputed.

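### A child whose StrataGraft-treated site is re-excised and then closes by Week 12 without autograft counts as a responder, because Tables 7 and 8 do not classify re-excision

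*Combined protocol and SAP*

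**What the plan says.** **Care of complications.** Protocol section 11.9.2 sets out a tiered plan for complications at the study burn sites. After topical and systemic treatment have failed, "the treated wound may be excised and the complication managed with topical or systemic therapy". Autograft is a separate and optional step: "Based on clinical judgment, autograft may be applied to the resulting wound bed to expedite wound closure". A treated site can therefore be excised again and never autografted.

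**Primary endpoint.** Section 5.1.2 gives "Percentage of subjects achieving confirmed complete closure of StrataGraft treatment sites on or before Week 12 without autograft placement". Table 7 words it for all sites: "Percentage of subjects achieving confirmed complete closure of all StrataGraft treatment sites on or before Week 12 without autograft placement". The Synopsis and section 12.3.1.1 agree. Autograft is the only treatment that disqualifies a closure.

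**Intercurrent events.** The Table 7 entry opens with "Early discontinuation due to" and gives six reasons, adverse event among them. The only data rule beside it counts missing or incomplete data as failure.

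**Ranked secondary endpoints.** Endpoint 2 (sites with confirmed closure) also excludes only autograft. Section 12.3.1.2 censors data collected after an autograft and has no matching rule for re-excision.

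**Data capture.** Section 11.4 records procedures in general. At site level, Table 2 footnote n names autograft as the only intervention to be assessed.

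**SAP.** The SAP is a memo for one enrolled subject. It plans listings only and adds no endpoint rule.

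**The concern.** The primary objective asks whether StrataGraft promotes closure and spares autograft. A wound excised again because of a complication has lost some or all of the treated surface. Its later closure is weaker evidence for the product than closure of an undisturbed site, yet the endpoint scores the two alike.

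The trial has one arm and tests against a fixed 50%. No control arm carries the same misclassification, so any such closures move the rate in one direction only: upward. The same holds for secondary endpoint 2, which is tested next but one in the hierarchy. For secondary endpoint 1, closed area measured after re-excision enters the mean, while area measured after autograft does not.

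**Working it through.** **1. Follow one child through the text.** A treated site develops a complication, fails topical and systemic treatment, and is excised again (11.9.2). No autograft is placed. The child attends all visits, every site is closed by Week 12, and closure is confirmed at least 2 weeks later and by Week 20.

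- Autograft placed? No, so the endpoint's exclusion does not apply.
- Discontinued early? No, so no Table 7 intercurrent event has occurred.
- Missing or incomplete data? No, so failure is not imputed.
- Censored under 12.3.1.2? No, because that rule is triggered by autograft.

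Result: responder.

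**2. Reproduce the plan's own figure.** Inputs from sections 12.1 and 12.3.1.1: n = 50 (or 40 in the younger cohort), null rate 50%, assumed rate 83%, success if the lower limit of the 95% normal-approximation interval reaches 50%.

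Lower limit = p − 1.96 × √(p(1 − p)/n)

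- 31/50: 0.62 − 1.96 × √(0.62 × 0.38/50) = 48.5%, fails
- 32/50: 0.64 − 1.96 × √(0.64 × 0.36/50) = 50.7%, passes
- 26/40: 0.65 − 1.96 × √(0.65 × 0.35/40) = 50.2%, the smallest passing count at n = 40

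Exact power is P(X ≥ r) for X ~ Binomial(n, 0.83): 99.97% at n = 50 (r = 32) and 99.84% at n = 40 (r = 26). The stated power of more than 90% is met. No stated number is in dispute.

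**3. Size per child.** 1/50 = 2 percentage points; 1/40 = 2.5 points.

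**4. Sensitivity.** The documents give no frequency. Let f be the percentage points of children who respond only through closure after re-excision; all values of f are assumptions. Column A is the chance of a positive study under the present wording if the closure rate without re-excision is exactly 50%: P(X ≥ r) at 0.50 + f. Column B is the power with re-excision counted as non-response, starting from 83%: P(X ≥ r) at 0.83 − f.

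| f (points) | A, n = 50 | A, n = 40 | B, n = 50 | B, n = 40 |
|---|---|---|---|---|
| 0 | 3.2% | 4.0% | 99.97% | 99.84% |
| 2 | 5.9% | 6.8% | 99.87% | 99.52% |
| 5 | 12.7% | 13.3% | 99.25% | 98.1% |
| 10 | 33.6% | 31.7% | 94.1% | 90.4% |
| 15 | 62.2% | 57.2% | 77.8% | 72.2% |

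The f = 0 row of column A is the exact one-sided error of the success rule itself. The lower rows are an upper range and not a forecast.

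**5. Distance from the threshold.** At the planned rate, 0.83 × 50 = 41.5 responders are expected. To fall to 31, about 41.5 − 31 = 10.5 children would have to be reclassified.

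**The case against.** **The case is rare.** This stands. The child must fail two tiers of treatment, be re-excised, receive no autograft although the wound was enrolled because autografting was indicated, and still close by Week 12. The contrast of 31 with 32 responders is true of any binary threshold and lies far from the planned rate.

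**The autograft was still avoided.** This stands in part. Sparing autograft is half of the objective, and counting such a child as a success resembles a treatment-policy strategy. That choice can be defended if it is stated; Table 7 does not state it.

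**Adverse-event discontinuation already covers it.** Section 6.6 does consider stopping the tissue product after an adverse reaction, and Table 7 lists adverse event as a reason for early discontinuation. But Table 7 attaches failure only to missing or incomplete data, and this child has none.

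**Three stronger readings** might be inferred, and the documents do not support them:

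- *That closure under another skin substitute is permitted and counted.* Section 4.1 says "Excised areas are usually closed with autograft or with allograft, xenograft, or other skin substitute until autograft is available or the wound spontaneously closes", but that is general background on burn care. Section 11.9.2 adds that "the investigator will use accepted standard of care (medication or surgery) as needed", without naming any such cover for a study site. The nearest item in section 8.2.2 is "Use of any investigational drug, device, or procedure administered as part of a research study", which does not reach marketed products. The documents neither permit nor prohibit such cover on a study site.
- *That these are closures the product did not produce.* This is unproven. Excision may be partial, and section 6.3 ascribes wound-bed conditioning to the product.
- *That the rate is overstated by a known amount.* Without a frequency, any range only restates its own assumption.

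**Conclusion.** The point holds for re-excision. The protocol foresees the event, and its endpoint and intercurrent-event rules, read together, score a later closure without autograft as a StrataGraft response. The possible bias is upward, at 2 percentage points per child at n = 50. The number of such children is unknown and probably small, and at the planned 83% the study would be unlikely to turn on it. The gap would matter most if the true rate lay near 50%.

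This is an inexpensive improvement to the endpoint definition and not a fault that undermines the design. It has no numerical consequence for this trial: the SAP memo reports one enrolled subject, no formal analysis and listings only. It would matter if the definition were used again.

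**What to change.** This is an analysis rule only; it changes no care.

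- **Tables 7 and 8:** list therapeutic re-excision of a StrataGraft treatment site, after Day 1 and before confirmed closure, as an intercurrent event counted as non-response for the primary endpoint and secondary endpoint 2.
- **Sensitivity analysis:** repeat both endpoints counting such closures as successes, so that the treatment-policy view is also reported.
- **Secondary endpoint 1:** handle data after re-excision as data after autograft are handled (censored under section 12.3.1.2). Scoring the site as 0% closed would be harsher than the plan is for autograft itself.
- **Data capture:** record the treatment site for each such procedure on the existing procedures form.
- **Other cover:** apply the same classification to any non-autograft skin cover placed on a study site, should it occur.

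The cost is short entries in two tables, site-level recording, one sensitivity analysis and a slightly less favourable response rate. By the calculation above, power stays above 90% at both n = 50 and n = 40 even if 10 points are reclassified from 83%.
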